11.2. Immunogenicity

Blood samples will be collected for assessment of ADA levels. Anti-Drug Antibody response during the entire study period and at each study assessment will be summarised according to ADA category and titre value for the Safety population with evaluable ADA results. A listing of the ADA test results will be produced.

[figure not shown]
For immunogenicity analysis, the presence of detectable (i.e., positive) ADAs against MEDI7352 will be reported. ADA results from each sample are reported as either positive or negative. In addition, the ADA titer result will be reported for samples confirmed positive for the presence of ADAs. A participant is defined as being ADA-positive if a positive ADA result is available at any time, including baseline and all post-baseline measurements, otherwise ADA negative.

The following ADA categories will be determined:

- ADA positive if a collected sample is tested positive at any time during the study, including baseline and/or post-baseline. (The percentage of these participants in a population is known as ADA prevalence).
- Treatment-emergent ADA positive (TE-ADA+): A positive post-baseline result and either of the following statements holds:
 - Baseline is ADA negative and at least one post-baseline assessment is ADA positive. This is called treatment-induced ADA positive.
 - o Baseline is ADA positive, and the baseline titre is boosted by greater than the variability of the assay (i.e., ≥X-fold increase, commonly 4-fold) at ≥1 post-baseline timepoint. This is called treatment-boosted ADA positive.

(The percentage of these participants in a population is known as ADA incidence)

- Only baseline positive if a collected sample is tested positive at baseline.
- Non-Treatment-emergent ADA positive (non-TE-ADA+): Participants who are ADA positive but not fulfilling the conditions for TE-ADA+.
- Treatment-emergent Persistently ADA positive: ADA negative at baseline and having at least 2 post-baseline ADA positive measurements with ≥16 weeks (112 days) between first and last positive, or an ADA positive result at the last available post-baseline assessment.
- Treatment-emergent Transiently ADA positive: ADA negative at baseline and at least one post-baseline ADA positive measurement and not fulfilling the conditions for persistently positive

[figure not shown]
• ADA positive post-baseline and positive at baseline.

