- Repeat for all scheduled post-baseline visits.
- A column for CC dosing (CC) will only be added if Stage 4 is initiated.

^[1] Baseline is defined as the last observation recorded prior to the first dose of treatment.

^[2] Number of subjects with at least one ADA assessment at the specific visit.

^[3] Number of subjects with a positive result at the specific visit. The denominator for all percentages is the number of subjects with an ADA result for each visit.

[figure not shown]
[figure not shown]

Table 14.3.5.20
Descriptive Summary of Anti-Drug Antibody Results and Titre by ADA Categories
Safety Population

	Salet	y Population			
	Placebo MEDI7352				
ADA Category	(N=xx)	CCI (N=xx)	CCI (N=xx)	CCI (N=xx)	All MEDI7352 (N=xx)
	/		,	,	
ADA positive at baseline and/or post-baseline (ADA					
prevalence)					
n/Nobs (%) [1] [2]	xx/xxx(xx.x%)	xx/xxx(xx.x%)	xx/xxx(xx.x%)	xx/xxx(xx.x%)	xx/xxx(xx.x%)
Maximum ADA Titre					
Median	XX.X	XX.X	XX.X	XX.X	XX.X
Q1, Q3	XX.X, XX.X	XX.X, XX.X	XX.X, XX.X	XX.X, XX.X	XX.X, XX.X
Min, Max	XX, XX	xx, xx	xx, xx	XX, XX	XX, XX
TE-ADA positive (ADA incidence) [5]					
n/Nobs (%) [1] [3]	xx/xxx(xx.x%)	xx/xxx(xx.x%)	xx/xxx(xx.x%)	xx/xxx(xx.x%)	xx/xxx(xx.x%)
Maximum ADA Titre					
Median	XX.X	XX.X	XX.X	XX.X	XX.X
Q1, Q3	XX.X, XX.X	XX.X, XX.X	XX.X, XX.X	XX.X, XX.X	XX.X, XX.X
Min, Max	xx, xx	xx, xx	xx, xx	xx, xx	XX, XX
Treatment Induced ADA Positive					
n/Nobs (%) [1] [3]	xx/xxx(xx.x%)	xx/xxx(xx.x%)	xx/xxx(xx.x%)	xx/xxx(xx.x%)	xx/xxx(xx.x%)
Maximum ADA Titre	· · · · ·	· · · · ·	•		, ,
Median	XX.X	XX.X	XX.X	XX.X	XX.X
Q1, Q3	XX.X, XX.X	XX.X, XX.X	XX.X, XX.X	XX.X, XX.X	XX.X, XX.X
Min, Max	xx, xx	xx, xx	XX, XX	xx, xx	XX, XX

[figure not shown]
Final 1.0 | 12-Jul-2023 | Page 117 of 205

Treatment-Boosted ADA Positive n/Nobs (%) [1] [3]	xx/xxx (xx.x%)				
Maximum ADA Titre					
Median	XX.X	XX.X	XX.X	XX.X	XX.X
Q1, Q3	XX.X, XX.X				
Min, Max	XX, XX				
Non-TE-ADA Positive					
n/Nobs (%) [1] [3]	xx/xxx(xx.x%)	xx/xxx(xx.x%)	xx/xxx (xx.x%)	xx/xxx(xx.x%)	xx/xxx(xx.x%)
Maximum ADA Titre	,		,	,	,
Median	XX.X	XX.X	XX.X	XX.X	XX.X
Q1, Q3	XX.X, XX.X				
Min, Max	XX, XX				
Both baseline and post-baseline positive					
n/Nobs (%) [1] [3]	xx/xxx(xx.x%)	xx/xxx (xx.x%)	xx/xxx (xx.x%)	xx/xxx(xx.x%)	xx/xxx (xx.x%)
Maximum ADA Titre	((()	()	()	(
Median	XX.X	XX.X	XX.X	XX.X	XX.X
Q1, Q3	XX.X, XX.X				
Min, Max	xx, xx				
Only baseline positive					
n/Nobs (%) [1] [4]	xx/xxx(xx.x%)	xx/xxx(xx.x%)	xx/xxx(xx.x%)	xx/xxx(xx.x%)	xx/xxx (xx.x%)

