Maximum ADA Titre	,	,	,	,	,
Median	XX.X	XX.X	XX.X	XX.X	XX.X
Q1, Q3	XX.X, XX.X				
Min, Max	XX, XX				
TE-persistently ADA positive [6]					
n/Nobs (%) [1] [3]	xx/xxx(xx.x%)	xx/xxx(xx.x%)	xx/xxx(xx.x%)	xx/xxx(xx.x%)	xx/xxx(xx.x%)
Maximum ADA Titre	` ,	, ,	, ,	, ,	` /
Median	XX.X	XX.X	XX.X	XX.X	XX.X
Q1, Q3	XX.X, XX.X				
Min, Max	XX, XX				
•	Ť	•	ŕ	•	*

Final 1.0 | 12-Jul-2023 | Page 118 of 205

TE-transiently ADA positive [7]					
n/Nobs (%) [1] [3]	xx/xxx(xx.x%)	xx/xxx(xx.x%)	xx/xxx(xx.x%)	xx/xxx(xx.x%)	xx/xxx(xx.x%)
Maximum ADA Titre					
Median	XX.X	XX.X	XX.X	XX.X	XX.X
Q1, Q3	XX.X, XX.X				
Min, Max	XX, XX				

ADA = Anti-Drug Antibodies; N = number of subjects per treatment group; TE-ADA = Treatment Emergent ADA; SD = standard deviation; Q1 = first quartile; Q3 = third quartile.

[figure not shown]
- [1] n represents the number of subjects satisfying the conditions of the specified ADA category
- [2] Nobs represents the number of subjects with any ADA result at baseline and/or post-baseline.
- [3] Nobs represents the number of subjects with an ADA result at baseline and at least one post-baseline ADA assessment.
- [4] Nobs represents the number of subjects with an ADA result at baseline.
- [5] TE-ADA positive is defined as either ADA negative at baseline and post-baseline ADA positive (Treatment Induced ADA Positive), or as ADA positive at baseline with pre-existing titre boosted during the study period (Treatment Induced ADA Positive). ADA incidence is the proportion of TE-ADA+ subjects in a population.
- [6] ADA negative at baseline and having at least 2 post-baseline ADA positive measurements with ≥16 weeks (112 days) between first and last positive, or an ADA positive result at the last available post-baseline assessment.
- [7] ADA negative at baseline and at least one post-baseline ADA positive measurement and not fulfilling the conditions for persistently positive.

Reference Listing: 16.2.9.19

Programming Notes:

- If a participant has more than 1 non-missing titre during the study, the maximum titre for each participant is summarized.
- Only present summary statistics if titre is available.
- If no positive results for a particular block of the table, then the summary statistics for the titres for that particular block would not appear.
- It is assumed that participants with a missing baseline ADA result are ADA negative at baseline.
- A column for column dosing (CC) will only be added if Stage 4 is initiated.

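### Table 14.3.5.20 (v1.0 shells): subjects with a missing baseline ADA result can enter the treatment-emergent counts but are left out of the denominator

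*SAP*

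**What the plan says.** The instructions are in the table shells v1.0 (12-Jul-2023), section 6.5, Table 14.3.5.20, and in SAP v1.1, section 11.2.

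- **Missing baseline.** A programming note under the table says: "It is assumed that participants with a missing baseline ADA result are ADA negative at baseline".
- **Numerator.** Footnote [1]: "n represents the number of subjects satisfying the conditions of the specified ADA category".
- **Denominator.** Footnote [3]: "Nobs represents the number of subjects with an ADA result at baseline and at least one post-baseline ADA assessment". It applies to the TE-ADA positive (incidence), treatment-induced, treatment-boosted, Non-TE-ADA positive, both-positive, TE-persistent and TE-transient rows.
- **Treatment-induced.** SAP section 11.2: "Baseline is ADA negative and at least one post-baseline assessment is ADA positive".
- **Non-TE-ADA positive.** SAP section 11.2: "Participants who are ADA positive but not fulfilling the conditions for TE-ADA" positivity.

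The prevalence row uses footnote [2], whose denominator takes anyone with an ADA result at any time. The baseline-only row uses footnote [4], which takes anyone with a baseline result.

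**The concern.** A reported proportion should have a numerator drawn from its denominator. Here the note gives a baseline status to subjects who have no baseline result, and footnote [3] then removes those subjects from Nobs. Nothing in the shell or in SAP section 11.2 limits n to subjects in Nobs, or says that an assumed negative counts as a baseline result.

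Immunogenicity is a secondary objective (SAP section 2.1.2), and section 11.2 identifies the TE-ADA positive percentage as ADA incidence. The rule as written can raise that figure but never lower it. Programmers who resolve the conflict differently would also report different incidences from the same data.

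**Working it through.** **Following one subject through the rules.** The subject has no baseline ADA result and one positive sample after dosing.

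1. The note makes the baseline negative.
2. The subject then meets the section 11.2 definition of treatment-induced, and so of TE-ADA positive. The subject is also either persistent or transient.
3. Footnote [1] counts the subject in n for those rows.
4. Footnote [3] needs a baseline result, so the subject is not in Nobs.

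The treatment-boosted and both-positive rows are not affected, because each needs an actual positive baseline.

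**Non-TE-ADA positive row.** A subject who is positive at baseline and has no later sample is ADA positive and cannot be treatment-emergent. The subject enters n, but footnote [3] needs a post-baseline assessment, so the subject is not in Nobs. This does not depend on the missing-baseline note.

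**Formulas.** The plan states no incidence figure to reproduce. Let:

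- Nb = subjects with baseline and post-baseline results
- m = subjects with post-baseline results only
- a = treatment-emergent positives among the Nb
- c = post-baseline positives among the m

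The possible proportions are:

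- As written: R = (a + c)/Nb
- Baseline required in both parts: A = a/Nb
- Missing taken as negative in both parts: B = (a + c)/(Nb + m)

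Then R/B = (Nb + m)/Nb = 1 + m/Nb, and R/A = 1 + c/a, which is also 1 + m/Nb when positivity is the same in both groups. Whenever c is at least 1, R exceeds both A and B. If m = 0, all three agree.

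**Illustration.** The 67 is the largest planned active-arm size in SAP section 3.2. It is an efficacy-evaluable count for stages 2 to 4, used here only for scale. The values of m and the 60% positivity are assumptions.

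| Nb | m | a | c | R (as written) | A | B | 1 + m/Nb |
|---|---|---|---|---|---|---|---|
| 67 | 0 | 40 | 0 | 40/67 = 59.7% | 59.7% | 59.7% | 1.00 |
| 64 | 3 | 38 | 2 | 40/64 = 62.5% | 38/64 = 59.4% | 40/67 = 59.7% | 1.05 |
| 60 | 7 | 36 | 4 | 40/60 = 66.7% | 36/60 = 60.0% | 40/67 = 59.7% | 1.12 |

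With 27 positives of 67 in all (about 40%) and 3 baselines missing, R = 27/64 = 42.2% against B = 27/67 = 40.3%.

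**When R passes 100%.** This needs a + c > Nb, which at a common positivity p means p > Nb/(Nb + m). The thresholds are 64/67 = 95.5%, 60/67 = 89.6% and, for an assumed arm with Nb = 5 and m = 1, 5/6 = 83.3%.

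**The case against.** **The text may have changed.** The note and footnotes are from the v1.0 shells. The v1.1 shells (31-Aug-2023) still list Table 14.3.5.20, but the supplied text stops before that shell. Version 1.1 did revise another denominator note, under Table 14.1.2. This stands: the point is established only for the v1.0 wording. The definitions in SAP section 11.2 carry over to v1.1.

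**A programmer may resolve the conflict sensibly.** Footnote [5] describes incidence as a proportion of subjects in a population, which implies a numerator inside its denominator. There are two ways to get there, and each cancels an instruction. If the assumed negative counts as a baseline result, the baseline condition in footnote [3] excludes nobody. If n is limited to Nobs, the missing-baseline note does nothing in this table. The shell has to choose.

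**The effect is small and visible.** The SAP gives no number of missing baselines. Safety analyses are descriptive (SAP section 9), Table 14.3.5.19 gives positivity by visit with a matching denominator, and Listing 16.2.9.19 shows each result. Each cell prints n/Nobs, so n above Nobs would be seen. This stands as a limit on importance; it does not make the ratio correct.

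**Missing as negative is a pre-specified assumption.** It may label pre-existing antibody as drug-induced, but it is a declared choice, and one of the two remedies keeps it. It is not counted here as a separate error.

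**Conclusion.** The point holds for the v1.0 shell. In four treatment-emergent rows the numerator is not contained in the denominator, and each baseline-missing subject who turns positive biases the percentage upward. The factor is 1 + m/Nb at a common positivity rate, about 1.05 for an assumed 3 of 67 missing. The Non-TE-ADA positive row has a separate mismatch of the same type.

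A reader might infer more than the documents support:

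- *Incidence will be inflated.* This needs at least one subject with a missing baseline and a later positive, and the literal rule to be programmed. The SAP does not say that any baseline will be missing.
- *Incidence will exceed 100%.* This is possible arithmetically, but only with near-universal positivity or a very small arm.
- *Small arms are inflated more.* The factor depends on m/Nb alone, so equal missing fractions give equal inflation. Only the effect of a single missing subject is larger in a small arm.
- *The population PK model relies on this proportion.* The interim plan (sections 5.2 and 6.2) describes modelling from PK and ADA datasets, not from table percentages.

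**What to change.** First check whether the v1.1 shell of Table 14.3.5.20 keeps the note and footnotes [1] and [3]. If it does, use one set of subjects for n and Nobs in the treatment-emergent rows, by either route:

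- **Keep the assumption.** Redefine Nobs for these rows as subjects with at least one post-baseline ADA result, with a missing baseline counted as negative. This keeps every subject with a post-baseline result.
- **Drop the assumption.** Remove the note and require a baseline result in n as well as in Nobs. The subjects without a baseline sample are then not counted in these rows.

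Under either route, require a post-baseline result in the Non-TE-ADA positive numerator. State the chosen rule in SAP section 11.2 too, because Table 14.3.1.5 groups adverse events by the same categories and refers to the SAP for their definitions.

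The cost is one footnote, one programming note and one sentence in the SAP. No data collection or other analysis changes.
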